2. OBJECTIVES

PRIMARY OBJECTIVES:

- Document the efficacy of the CyberKnife® procedure, where efficacy is defined by biochemical Disease-Free Survival (bDFS), using Phoenix and ASTRO definitions, at 5 years.

- Compare the CyberKnife® Stereotactic Radiosurgery System bDFS rate to published HDR monotherapy bDFS rates reported in the literature.

SECONDARY OBJECTIVES:

- Measure rates of acute and late grade 3-5 gastrointestinal and genitourinary toxicity observed during the five years following CyberKnife® Stereotactic Radiosurgery System for prostate cancer. Acute toxicity will be defined as occurring within 90 days from completion of treatment. Late toxicity will be defined as occurring more than 90 days from completion of treatment. It is graded based upon Common Terminology Criteria for Adverse Events (CTCAE), v3.0 and RTOG/ECOG definitions (see appendix 5).
- Measure rates of local failure, distant failure, clinical disease-free survival, disease-specific survival, and overall survival
- Examine Quality of Life (QOL) in generic and organ-specific domains

3. DEVICE

Accuray, Inc. (Sunnyvale, CA), received FDA clearance in July 1999 to provide treatment planning and image guided stereotactic radiosurgery and precision radiotherapy for lesions, tumors and conditions of the brain, base of skull and cervico-thoracic spine, head and neck using the CyberKnife®. On August 10, 2001, Accuray, Inc. received 510(k) FDA clearance (510(k) number K011024) to provide treatment planning and image-guided stereotactic radiosurgery and precision radiotherapy for lesions, tumors, and conditions anywhere in the body when radiation treatment is indicated.

4. PRETREATMENT EVALUATION

- 4.1. Complete history and physical exam
- 4.2. DRE findings from urologist or radiation oncologist
- 4.3. Assessment of performance status
- 4.4. Histological evaluation of prostate biopsy with assignment of Gleason score
- 4.5. Evaluation of the pelvic lymph nodes with CT or MRI is optional
- 4.6. Serum PSA. Laboratory evaluation must be done within 90 days prior to treatment
- 4.7. CBC, platelets, serum BUN and creatinine
- 4.8. The prostate volume may be obtained by prior transrectal ultrasound. A CT or MRI-based prostate volume measurement will also be acceptable (specify which modality).
- 4.9. Patient questionnaires (see Appendix VI).
 - 4.9.1. AUA questionnaire
 - 4.9.2. EPIC-26 questionnaire
 - 4.9.3. SHIM questionnaire

5. PATIENT SELECTION & ELIGIBILITY

- 5.1. Patient must be \geq 18 years of age.

- 5.2. Histologically proven prostate adenocarcinoma
 - 5.2.1. Gleason score 2-10 (reviewed by reference lab)
 - 5.2.2. Biopsy within one year of date of registration
- 5.3. Clinical stage T1b-T4, N0-Nx, M0-Mx (AJCC 7th Edition)
 - 5.3.1. T-stage and N-stage determined by physical exam and available imaging studies (ultrasound, CT, and/or MRI; see section 4.5)
 - 5.3.2. M-stage determined by physical exam, CT or MRI. Bone scan not required unless clinical findings suggest possible osseous metastases.
- 5.4. PSA \leq 50 ng/ml, CBC, platelets, BUN, creatinine prior to treatment
- 5.5. Patients belonging in one of the following risk groups:
 - 5.5.1. Intermediate: CS T2b-c and Gleason \leq 6 and PSA \leq 10, or CS T1b-T2b, and Gleason 7 and PSA \leq 10 ng/ml, or Gleason \leq 6 and PSA 11-20 ng/ml
 - 5.5.2. High: CS T3-4, Gleason score >7 and PSA \leq 50
- 5.6. Prostate volume: \leq 100 cc
 - 5.6.1. Determined using: volume = $\pi/6 \times$ length \times height \times width
 - 5.6.2. Measurement from MRI, CT or ultrasound prior to registration.
- 5.7. ECOG performance status 0-1
- 5.8. No prior prostatectomy or cryotherapy of the prostate
- 5.9. No prior radiotherapy to the prostate or lower pelvis
- 5.10. No implanted hardware or other material that would prohibit appropriate treatment planning or treatment delivery, in the investigator's opinion.
- 5.11. No chemotherapy for a malignancy in the last 5 years.
- 5.12. No history of an invasive malignancy (other than this prostate cancer, or basal or squamous skin cancers) in the last 5 years.
- 5.13. Completion of patient questionnaires in section 4.7.
- 5.14. Consent signed.

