3) Per investigator decision and patient discussion, with consideration of age, performance status, medical co-morbidities, Gleason score and other disease features (Gleason score 4+3 vs. 3+4). Strong recommendation is made for consideration of combined modality therapy in intermediate risk and certainly "high intermediate" risk disease as defined by Gleason score 4+3 disease, more than 50% positive cores, and/or PSA velocity of more than 2ng/ml in the year preceding tissue diagnosis, given survival benefit of short term ADT per randomized data in intermediate risk disease. CK SBRT monotherapy would typically be appropriate only for low volume GS 3+4 disease with no other adverse features.

ELIGIBILITY CHECKLIST

(Y) Is there histologically proven prostate adenocarcinoma, biopsy within one year of enrollment?

What is the Gleason Score?

(T1b-4) What is the clinical T-stage? (AJCC 7th Edition)

(Y) Is the patient clinical Nx or N0, and Mx or M0?

(0-50) PSA evaluated 90 days prior to radiation therapy or the most recent PSA evaluated prior to ADT, whichever is applicable

(I, H) Does the patient fall into one of these risk groups (AJCC 6th Edition):
- Intermediate: CS T2b-c, Gleason ≤ 6 , PSA ≤ 10 , or CS T1b-T2a, and Gleason 7, PSA ≤ 10 ng/ml, or Gleason ≤ 6 , PSA 11-20 ng/ml
- High: CS T3-4 or Gleason > 7 and PSA ≤ 50

(Y) Is the prostate volume ≤ 100 cc?

(0-1) What is the ECOG performance status?

(N) Has the patient undergone prostatectomy or cryotherapy of the prostate?

(N) Has the patient had radiotherapy to the prostate or lower pelvis?

(N) Is there implanted hardware near the planning target volume that would prohibit appropriate treatment planning or treatment delivery in the investigator's opinion?

(N) Has the patient had chemotherapy for a malignancy in the last 5 years?

(N) Has the patient had an invasive malignancy (other than this prostate cancer, or basal or squamous skin cancers) in the last 5 years?

(n/a, Y) Has the patient's androgen function been ablated during the past 2 months?

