Based on the data provided in the reports summarized above, and adding a PSA DFS degradation factor to the Gamma West series to compensate for their short median follow-up, the average calculated 5 year HDR monotherapy ASTRO-based PSA DFS is 98% for favorable prognosis, 82% for intermediate prognosis and 59% for unfavorable prognosis cases. There are too few Phoenix-based PSA DFS results to project a meaningful Phoenix-based HDR monotherapy PSA DFS efficacy result.

It is anticipated that the case mix in this study will be approximately 75% intermediate, and 25% high risk prognosis cases, leading to a predicted 5 year PSA DFS rate of 85%-90% for intermediate risk patients, and 75%-80% for high risk patients based on HDR brachytherapy boost trial. **Table 2. Toxicity review for HDR-Monotherapy for Prostate Cancer**

HDR Details	Institution	# pts	Median f/u	>= Gd 3 toxicity		
				Total (%)	GI (%)	GU (%)
6-7.25Gy x 6	CA Endocurie ³⁰	117	3.3	3	0	3
9.5Gy x 4	Beaumont ³¹	95	4.2	8	0	8
7.5Gy x 6	Texas Tech ³²	145	5	5 – 8*	1	4 – 7*
6.5Gy x 6	Gamma West (SLC) ³³	328	1.2	1	0	1
6Gy x 8-9	Osaka (Japan) ³⁴	111	2.25	7	1	6
Totals		796	2.4	6	0 -1	5

*3% acute and 4% chronic grade 3 GU toxicity – It is unclear to what degree acute and chronic grade 3 GU toxicity populations overlap in this study.

To confirm our hypothesis that CyberKnife® radiosurgery may be made to resemble a “noninvasive HDR dosimetry delivery system,” in addition to simply creating equivalent dosimetry, it is necessary to show clinical equivalence both in terms of efficacy and toxicity. Due to short median follow-up, the incidence of >= grade 3 late toxicity is likely underestimated. We project that the incidence of late toxicity will increase by approximately 50% when all data reach 5 years maturity, yielding a projected cumulative 5 year HDR monotherapy grade 3 toxicity incidence of 9% (7-8% GU; 1-2% GI). In this study, biochemical disease-free survival (ASTRO and Phoenix definition), freedom from local recurrence, freedom from distant relapse, clinical disease-free survival, disease-specific survival and overall survival will be recorded. The incidence of grade 3 or higher toxicity and the effect of CyberKnife® radiosurgery on bladder, bowel, and sexual function will be followed and monitored using standardized, patient self-administered questionnaires²⁸ and compared with results published in peer-reviewed literature for other prostate cancer therapeutic modalities.²⁹

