8. TREATMENT: CYBERKNIFE® RADIOSURGERY

- 8.1. Intermediate risk patients will be treated with either: CyberKnife® SBRT boost of 21 Gy (7 Gy X 3) followed by prostate/SV IMRT 45-50.4 Gy (treatment planning and delivery per current standards of care); or CyberKnife® SBRT monotherapy 36.35Gy (7.27Gy x 5). Short term Androgen Deprivation Therapy (4-6 months per standards of care) is strongly recommended for all intermediate risk patients.

High risk patients will be treated with CyberKnife® boost of 21 Gy (7 Gy X 3) followed by whole pelvis IMRT 45-50.4 Gy (treatment planning and delivery per current standards of care). Short or long term ADT (6 months up to 3 years per current standards of care) is strongly recommended for high risk patients.

Standards of care are based on National Comprehensive Cancer Network guidelines. Per investigator decision and patient discussion, the appropriate treatment plan will be determined for each patient based on their risk group outlined by these guidelines. Patient age, performance status, medical comorbidities, Gleason score and other disease features (Gleason score 4+3 vs. 3+4) will be taken into consideration. Strong recommendation is made for consideration of combined modality therapy for patients with : Gleason score 4+3 disease, more than 50% positive cores, and/or PSA velocity of more than 2ng/ml in the year preceding tissue diagnosis, given survival benefit of short term ADT. CyberKnife® SBRT monotherapy would typically be appropriate only for low volume GS 3+4 disease with no other adverse features.

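### The risk groups in Section 5.5 and in the eligibility checklist leave T1-T2, Gleason 7 or lower men inside the trial's outer limits without a group, so eligibility switches off and on again as PSA or Gleason rises

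*Combined protocol and SAP*

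**What the plan says.** Section 5 sets outer limits of stage T1b to T4, Gleason 2 to 10 and, in 5.4, "PSA \leq 50 ng/ml, CBC, platelets, BUN, creatinine prior to treatment". Section 5.5 then requires membership of a listed group. Its intermediate group has three limbs. The first is "CS T2b-c and Gleason \leq 6 and PSA \leq 10"; the other two are "CS T1b-T2b, and Gleason 7 and PSA \leq 10 ng/ml, or Gleason \leq 6 and PSA 11-20 ng/ml". Its high group reads "High: CS T3-4, Gleason score >7 and PSA \leq 50".

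The Eligibility Checklist asks "Does the patient fall into one of these risk groups". Its T2b-c limb matches Section 5.5, but its other intermediate limbs are "CS T1b-T2a, and Gleason 7, PSA ≤ 10 ng/ml, or Gleason ≤ 6 , PSA 11-20 ng/ml", so the Gleason 7 limb ends at T2a and not T2b. Its high group joins T3-4 and Gleason above 7 with 'or', where Section 5.5 has a comma.

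Section 6.2 allows registration only once all eligibility criteria are met and points to the checklist, so both texts govern entry.

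Section 8.1 offers monotherapy only to intermediate-risk men and whole-pelvis IMRT with boost to high-risk men. It also says that "the appropriate treatment plan will be determined for each patient based on their risk group outlined by these guidelines", meaning the NCCN guidelines. Section 11.1 plans its estimates by treatment received.

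**The concern.** The PSA 11-20 limb requires Gleason 6 or lower, and the Gleason 7 limb requires PSA of 10 or lower. Neither high-risk wording lets PSA alone place a T1-T2 man in a group. Men between these limbs satisfy every other criterion and still belong nowhere.

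A site then has two courses. It can exclude them, which removes Gleason 7 combined with PSA above 10 or with T2c and so narrows the intermediate group towards men with a single adverse factor. Or it can label them case by case. Under Section 8.1 the label bears on the regimen, and under Section 11.1 the regimen decides the analysis group. Either way, the population behind each 5-year rate is not the one a reader would take from the outer limits. That matters because a primary objective compares bDFS with published HDR rates, which Section 1 splits by prognosis (98%, 82% and 59%).

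**Working it through.** **The plan's own figures.** Section 11.1 gives 32 men (expected rate 80%) and 40 men (70%) for a 95% interval of total width 0.30. The exact (Clopper-Pearson) width at 80% is 0.3034 with n = 31 and 0.2985 with n = 32. At 70% it is 0.3036 with n = 39 and 0.2997 with n = 40. Both sizes reproduce and are unaffected by this point.

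**Grid.** Stages T1b, T1c, T2a, T2b, T2c, T3, T4 (7) × Gleason ≤6, 7, 8-10 (3) × PSA ≤10, between 10 and 11, 11-20, >20 to 50 (4) = 84 cells, all inside the outer limits.

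**Readings tested.** The checklist as written, and Section 5.5 with the high-risk comma read as 'or' and as 'and'. Each was run with the PSA 11-20 limb open to any stage, and again with it confined to the stage range stated just before it.

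| Reading | Cells with no group, of 84 |
|---|---|
| Section 5.5, comma = or | 29-30 |
| Checklist | 30-32 |
| Section 5.5, comma = and | 63-66 |

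**Gaps common to every reading: 29.** Three are T1b, T1c and T2a with Gleason ≤6 and PSA ≤10. These look like low-risk men left out on purpose, and they are set aside. The other 29 − 3 = 26 are all T1-T2 with Gleason ≤7:

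- Gleason 7, PSA above 10: 5 stages × 3 bands = 15.
- T2c, Gleason 7, PSA ≤10: 1 more, so T2c with Gleason 7 has no group at any PSA.
- Gleason ≤6, PSA between 10 and 11: 5 stages × 1 band = 5.
- Gleason ≤6, PSA above 20 to 50: 5 stages × 1 band = 5.

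15 + 1 + 5 + 5 = 26. Within T1b-T2c, Gleason 7 alone has 16 of 20 cells unassigned under Section 5.5 (taken as T1b-T2b). Under the checklist it has 17, because T2b with PSA ≤10 is lost too.

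**Direction of the rule.** These sequences use only the trial's own text:

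- T2b, Gleason 6, Section 5.5: PSA 9.9 in, 10.5 out, 11 in. This holds under every reading of 5.5. On the checklist it holds if the PSA 11-20 limb is not confined to T1b-T2a.
- T1c, PSA 15, checklist: Gleason 6 in, 7 out, 8 in.
- T2c, PSA 6, checklist: Gleason 6 in, 7 out, 8 in.

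Milder and worse disease is admitted while the middle is refused.

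**Effect of contiguous bands alone.** Changing 11-20 to >10 to 20 closes the 5 Gleason ≤6 cells between 10 and 11 if that limb is open to any stage. The other 26 − 5 = 21 remain and need a decision.

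**The case against.** The strongest reply is that narrow entry is a legitimate choice. The outer limits apply jointly with 5.5, PSA up to 50 is used by the high group, and the sponsor may have meant to exclude Gleason 7 with PSA above 10. Read literally, the result is exclusion and not ad hoc labelling. This stands in part: the documents do not settle intent, and ad hoc labelling is a risk, not a documented practice. It does not explain a rule that reverses as PSA rises, or one that takes Gleason 6 and 8 but not 7, and no rationale is given.

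Cell counts also overstate the matter. The 10-to-11 sliver carries the same weight as bands of 10 or 30 ng/ml. With three contiguous bands, Gleason 7 has 11-12 of 15 cells unassigned. The sliver also disappears if PSA is recorded in whole numbers. That is fair as to weight, but the protocol gives no rounding rule for PSA, although Section 8.4.4 gives one for volume percentages, and whole numbers would close only that gap.

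A reader might infer that the intermediate group describes only favourable disease. It does not. It admits any Gleason 7 including 4+3, puts no limit on positive cores or PSA velocity, and takes T2b-c or PSA 11-20 with Gleason ≤6. The treatment note printed just before the checklist itself calls the first three 'high intermediate'.

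A reader might also infer that a planned intermediate-risk rate is inflated against the HDR series. Section 11.1 plans no analysis by risk group, and Section 1's "predicted 5 year PSA DFS rate of 85%-90% for intermediate risk patients, and 75%-80% for high risk patients" is a background prediction. The documents do not say how the HDR series defined intermediate risk, so neither direction nor size can be shown.

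**Conclusion.** The point holds for T1-T2 men with Gleason 7 or lower. Both governing texts leave the same 26 of 84 cells without a group under every reading tried, and the entry rule is non-monotone as written. The qualifier matters. On the checklist, T1-T2 men with Gleason 8-10 are high risk at any PSA up to 50, as are T3-4 men with Gleason 7. Those become gaps only if the comma in Section 5.5's high group means 'and'.

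The consequence is a narrowed intermediate group, or labelling left to the site with a possible effect on regimen and analysis group. Because 8.1 assigns treatment by guideline risk groups that the protocol does not reproduce, a man's eligibility group and treatment group need not agree even where 5.5 does classify him.

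The share of men affected is unknown, since no joint distribution of stage, Gleason and PSA is given. The conclusion assumes that the limbs are applied literally and that PSA may take values between 10 and 11. It does not assume that any outside classification is correct.

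**What to change.** 1. Make the PSA bands contiguous: ≤10, >10 to 20, >20 to 50, with '>10 to 20' replacing '11-20'.
2. Use one identical table in Section 5.5 and the checklist, in which the sponsor marks every combination of T-stage, Gleason and PSA as intermediate, high or ineligible. Completing it also settles T2a versus T2b for Gleason 7 and 'or' versus the comma in the high group.
3. If the remaining exclusions are intended, say so and describe the reported population accordingly in the comparison with HDR rates.
4. Reconcile the Section 5.5 risk groups with the guideline risk groups that Section 8.1 uses to assign treatment. Which classification should govern treatment is for the sponsor to decide.

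The cost is one amendment to the protocol and checklist. Men already enrolled can be re-classified from recorded stage, Gleason score and PSA; some may be re-labelled or reported as deviations. The sample sizes do not change.

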6. REGISTRATION PROCEDURES

- 6.1. PHYSICS QUALITY ASSURANCE shall at a minimum include:
 - 6.1.1. ABSOLUTE DOSIMETRY: Must document CyberKnife® absolute calibration in water according to AAPM TG51. Site must also document that, within the last year, photon beam output has been verified by the Radiological Physics Center (RPC).
 - 6.1.2. DAILY QA: must provide documentation that, for the prior month, the following has been performed daily:
 - 6.1.2.1.1. At least 3000 MUs delivered daily for machine warm-up (per Accuray)
 - 6.1.2.1.2. Temperature and atmospheric pressure recorded, output calibration performed, and new output factor recorded.
 - 6.1.2.1.3. Position of laser at perch position verified to be within 1mm of floor reference point.
 - 6.1.3. MONTHLY QA: must provide documentation that the following monthly QA is being performed:
 - 6.1.3.1.1. Beam output in phantom verified as \pm 1% of specified output

- 6.1.3.1.2. Beam energy constancy verified by ion chamber measurements at two depths in phantom, using 60mm collimator and 80cm SAD. Ratio should be within +/- 2% of the output ratio determined from TPR tables.
- 6.1.3.1.3. Beam symmetry measured by water scanning system or by radiographic (XV) or gafchromic (EBT or MD55) film. Beam symmetry should not exceed +/- 2% using area method.
- 6.1.3.1.4. Fiducial tracking end-to-end tests using ball-cube phantom. Maximum tracking radial error should be <0.95mm, with left-right, ant-post, and inf-sup errors not exceeding 0.8mm.
- 6.1.3.1.5. Laser – radiation field congruence measured using XV or EBT film in phantom under standard conditions (SAD = 80cm, 5mm build-up material and 60mm collimator), with laser center marked by a pin. Displacement, evaluated using imaging software or graph paper, should not exceed 1mm.
- 6.1.4. Daily and monthly QA as described above may be recorded in the CyberKnife® Robotic Radiosurgery System QA Log Book, or in other documents, and should continue throughout the enrollment period.

6.2. PATIENT REGISTRATION: Patients may be registered only after all eligibility criteria are met: see Eligibility Checklist above, and Inclusion Criteria and Exclusion Criteria CRFs (Case Report Forms). After the patient signs the Consent Form the patient is enrolled in the study, and scheduled for treatment. The pre-treatment CRFs are then filled out by the investigator and/or research associate. This data is retained in the patient's chart located in the research office. The date of registration may be the date the consent was signed. Fiducials must be placed within 60 days, and the first fraction of radiosurgery must be administered within 90 days of registration.

7. PATHOLOGY

- 7.1. Pathology procedures will be conducted in accordance with institutional policy.
- 7.2. Pathology Evaluation: Slides/blocks from the pre-treatment diagnostic prostatic biopsy will be reviewed by signing pathologist to confirm the diagnosis and Gleason score. Other histopathologic features, including extent of tumor in the biopsies, the number of biopsies positive and perineural invasion, shall be recorded.

7.3. Central Review: encouraged but not required.

8. TREATMENT: CYBERKNIFE® RADIOSURGERY

- 8.1. Intermediate risk patients will be treated with either: CyberKnife® SBRT boost of 21 Gy (7 Gy X 3) followed by prostate/SV IMRT 45-50.4 Gy (treatment planning and delivery per current standards of care); or CyberKnife® SBRT monotherapy 36.35Gy (7.27Gy x 5). Short term Androgen Deprivation Therapy (4-6 months per standards of care) is strongly recommended for all intermediate risk patients.

High risk patients will be treated with CyberKnife® boost of 21 Gy (7 Gy X 3) followed by whole pelvis IMRT 45-50.4 Gy (treatment planning and delivery per current standards of care). Short or long term ADT (6 months up to 3 years per current standards of care) is strongly recommended for high risk patients.

Standards of care are based on National Comprehensive Cancer Network guidelines. Per investigator decision and patient discussion, the appropriate treatment plan will be determined for each patient based on their risk group outlined by these guidelines. Patient age, performance status, medical comorbidities, Gleason score and other disease features (Gleason score 4+3 vs. 3+4) will be taken into consideration. Strong recommendation is made for consideration of combined modality therapy for patients with : Gleason score 4+3 disease, more than 50% positive cores, and/or PSA velocity of more than 2ng/ml in the year preceding tissue diagnosis, given survival benefit of short term ADT. CyberKnife® SBRT monotherapy would typically be appropriate only for low volume GS 3+4 disease with no other adverse features.

8.2. FIDUCIAL PLACEMENT: All patients will have fiducial seeds measuring 3-5 mm placed in the prostate prior to treatment planning. A minimum of three fiducial seeds will be placed under transrectal ultrasound guidance, using either transperineal or transrectal approach, with local anesthesia and/or sedation as required. The use of linked fiducials is encouraged, since they may migrate less than individually placed fiducials. The physician will place seeds such that they are visible (and not superimposed) on CyberKnife® orthogonal imaging, are not collinear, and ideally are separated by 2 cm or more. Fiducials will be placed as an outpatient procedure. Local anesthetic injection, oral or intravenous sedating medication, oral or intravenous pain medication and prophylactic antibiotics may be given at the discretion of the investigator to maximize the safety and comfort of fiducial placement. At least three seeds must be usable for tracking during treatment. If an interim analysis shows unacceptable fiducial migration with a specific technique or type of fiducial, further use of this technique or type of fiducial may be prohibited by the Principal Investigator. SpaceOAR Hydrogel can be used per physician discretion. SpaceOAR Hydrogel reduces rectal injury in men receiving prostate cancer radiation therapy (RT) by acting as a spacer – pushing the rectum away from the prostate.

SpaceOAR hydrogel is an option for men who undergo radiation treatment for prostate cancer. It acts as a spacer providing space between the rectum and the prostate, making it much less likely that the rectum is exposed to radiation. It is injected into place prior to the start of radiation treatment. Patients may be awake or asleep under general anesthesia for the procedure. SpaceOAR hydrogel is minimally invasive, remains stable during radiation therapy and then is gradually absorbed by the body after radiation therapy has been completed.

8.3. TREATMENT PLANNING IMAGING:

- 8.3.1. To allow fiducial stabilization and resolution of swelling, planning studies will be imaged \geq 7 days after fiducial placement. Alpha Cradle or a similar immobilization device will be used as needed.
- 8.3.2. CT scans will be taken for treatment planning. CT slices will be 1 – 1.5mm,

with 250-512 slices taken centered at the prostate. The imaging sets will be downloaded to the CyberKnife® treatment planning system to develop the radiosurgery treatment plan.

8.3.3. If not medically contraindicated, all patients will undergo MRI imaging to determine the anatomical borders of the prostate. This study will be fused to the treatment planning CT. No endorectal coil allowed.

8.3.4. URETHRAL IDENTIFICATION:

The planning CT and MRI scans will be done with a Foley catheter in place to define the natural course of the urethra through the CTV. To improve comfort and minimize inconvenience to the patient, if possible, CT and MRI planning studies will be done consecutively.

8.3.5. Prior to treatment planning imaging, the patient will follow the bowel/urinary preparation procedures used for treatment (see section 8.4.2).

8.4. CYBERKNIFE® TREATMENT PLANNING:

8.4.1. TREATMENT PLANNING PROCEDURES: Inverse planning using the CyberKnife® planning system will be employed. The treatment plan used for each treatment will be based on an analysis of the volumetric dose including dose-volume histogram (DVH) analyses of the PTV and critical normal structures. Any beams entering through a hip prosthesis on their way to the planning target volume shall be turned off. Number of paths and beams used for each patient will vary and will be determined by the selected individual treatment plan. A priority will be placed on reducing overall treatment time, number of non-zero beams and total monitor units without compromising the dosimetric limits listed in section 8.3.4. All plans are expected to require no more than 2 hours per treatment, no more than 300 non-zero beams and no more than 95,000 monitor units for all fractions.

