1.12. The feasibility of CyberKnife® for treating localized prostate cancer was first described by King at Stanford University. Their phase I protocol delivered 36.25Gy in 5 fractions of 7.25Gy. In a recent report of acute and 18-month late toxicity in 26 “low-risk” patients, no patient experienced grade 3 or 4 acute or late toxicity, and only one patient experienced a grade 2 late morbidity (urethral stricture). Toxicity was less than that reported in MD Anderson’s external beam dose escalation trial. Mean PSA 18 months after treatment was 0.22ng/m²⁵. Similar excellent results have also been reported by Jabbari et al. from the University of California for both CyberKnife® monotherapy and boost post whole pelvic radiation therapy³, and King and Freedman using the original Stanford fractionation of five fractions when used as monotherapy⁴.

1.13. Another potential benefit of CyberKnife® radiosurgery relative to HDR brachytherapy is better preservation of potency, even if the radiation distribution is essentially identical between these modalities. This is so because needle trauma has been identified as a potentially significant contributory factor to erectile dysfunction with brachytherapy, including HDR-based monotherapy technique, presumably due to direct physical injury to the neurovascular bundle and/or bulb of the penis, particularly when greater than 13 needle insertions are performed.²⁷ By comparison, CyberKnife® radiosurgery is noninvasive, and so removes this particular erectile dysfunction risk factor.

Table 1. 5-Year bDFS Outcomes for HDR-Monotherapy for Prostate Cancer

HDR Details	Institution	#pts	Median f/u yrs	Phoenix	ASTRO
6–7.25 Gy x 6	CA Endocurie ³⁰	117	3.3		97%
9.5 Gy x 4	Beaumont ³¹	95	4.2		98%
7.5 Gy x 6	Texas Tech ³²	145	5		90%
6.5 Gy x 6	Gamma West – Fav. (SLC) ³³	209	1.2	96%*	99%*
	Gamma West – Int. ³³	119	1.2	89%*	89%*
6 Gy x 8-9	Osaka (Japan) ³⁴	111	2.25		70%†
Totals		796	2.4		90%

*3 year result; Projecting constant failure rate in this series to 5 years yields 98% and 82% ASTRO-definition PSA DFS for favorable and intermediate risk cases, respectively. †Predominantly unfavorable prognosis cases in this series; 5 year local control is 97%.

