8.4.4. **DOSE SPECIFICATIONS:** All specified doses are for the entire treatment course. All volume percentages are rounded to the nearest tenth of a percent for consistency, i.e. a volume of 0.02% shall be recorded as 0.0%.

8.4.4.1. The **PRESCRIPTION DOSE** of 36.25Gy in 5 fractions for monotherapy or 21Gy in 3 fractions for boost will be delivered in <10 days, with > 95% of the PTV encompassed within the prescription isodose volume. Maximum PTV dose 130% prescription dose.

8.4.4.2. **CONFORMALITY INDEX FOR NORMAL TISSUES:** The ratio of the prescription isodose volume to the PTV will be ≥ 1.0 and ≤ 1.5 . Minor variation: ≤ 0.99 or $\geq 1.51 - 2.0$

8.4.4.3. **DOSE OBJECTIVES:** The following table outlines the target and normal tissue objectives:

Organ	Constraint	21Gy in 3Fx	36.25Gy in 5 Fx
PTV	Dose Normalization	70 - 80%	70 - 80%
PTV	Dose min 95%	≥ 21 Gy	≥ 36.25 Gy
PTV	Dose Max	26.25 - 30 Gy	45.31 - 51.79 Gy
Prostate	Dose Min to 100%	≥ 21 Gy	≥ 36.25 Gy
Rectum	Dose Max to 1 cc	≤ 22.05 Gy	≤ 38.06 Gy
Rectum	3 cc	≤ 19.95 Gy	≤ 34.4 Gy
Rectum	10%	≤ 18.9 Gy	≤ 32.625 Gy
Rectum	20%	≤ 16.8 Gy	≤ 29 Gy
Rectum	50%	≤ 10.5 Gy	≤ 18.125 Gy

Bladder	Dose Max to 1 cc	<= 22.05 Gy	<= 38.06 Gy
Bladder	10%	<= 18.9 Gy	<= 32.625 Gy
Bladder	50%	<= 10.5 Gy	<= 18.125 Gy
Penile Bulb	Dose Max to 1 cc	<= 21 Gy	<= 36.25 Gy
Penile Bulb	3 cc	<= 11.34 Gy	<= 20 Gy
Femoral Heads	Dose Max to 1 cc	<= 17.01 Gy	<= 30 Gy
Femoral Heads	10 cc	<= 11.34 Gy	<= 20 Gy
Urethra	Dose Max to 0.03 cc	<= 22.5 Gy	<= 38.78 Gy
Bowel	20 cc	<= 24 Gy	<= 25 Gy
Penis/Testicles	1 cc	as low as possible	as low as possible

8.4.4.4.

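### Section 8.4.4.1 caps the PTV maximum at 130% of prescription but the 8.4.4.3 table allows up to 142.9%; separately, section 8.1 gives monotherapy as 36.35 Gy where the prescription clause and table use 36.25 Gy

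*Combined protocol and SAP*

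**What the plan says.** **PTV maximum.** The prescription clause, 8.4.4.1, ends with an upper limit: "Maximum PTV dose 130% prescription dose". The objectives table in 8.4.4.3 gives a normalization range of 70-80% for both regimens. It gives a PTV maximum of "45.31 - 51.79 Gy" for monotherapy and 26.25 to 30 Gy for boost.

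**Monotherapy dose.** Section 8.1, which assigns regimens by risk group, gives "CyberKnife® SBRT monotherapy 36.35Gy (7.27Gy x 5"). Section 8.4.4.1 sets a prescription dose "of 36.25Gy in 5 fractions for monotherapy or 21Gy in 3 fractions for boost", and the table's monotherapy column is headed "36.25Gy in 5 Fx". The precedent described in section 1.12 is the same as the prescription clause: "Their phase I protocol delivered 36.25Gy in 5 fractions of 7.25Gy". The boost dose is 21 Gy in three fractions throughout.

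**The concern.** Section 8.4.4 is where a planner finds the limits that a plan must meet. Its clause and its table give different ceilings for the same quantity, and no order of precedence is stated. A plan normalized at, say, 72% is acceptable by the table and a deviation by the clause. For the conformality index, 8.4.4.2 defines a minor variation. No such grade is defined for the PTV maximum.

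The cross-references do not help. Section 8.4.1 sends the reader to 8.3.4 for the dosimetric limits, and that section covers urethral identification. Note 2 in section 12 points to 8.3.2, which covers CT imaging.

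The dose in 8.1 is a separate and smaller matter: the protocol states two monotherapy prescriptions. Because 7.27 x 5 does equal 36.35, someone reading 8.1 alone would see nothing amiss.

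At stake is whether treatment is planned and recorded to one standard. The estimation of biochemical disease-free survival is not affected.

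**Working it through.** **Inputs.** Prescription 36.25 Gy (monotherapy) and 21 Gy (boost), and the 130% cap: 8.4.4.1. Normalization 70-80% and the PTV maxima: 8.4.4.3 table. Monotherapy 36.35 Gy as 7.27 Gy x 5: 8.1. Alpha/beta of 1.5 Gy: 1.7.

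**Step 1: reproduce the table's PTV maxima.** Maximum = prescription / normalization.
- Monotherapy: 36.25/0.80 = 45.31 Gy; 36.25/0.70 = 51.79 Gy.
- Boost: 21/0.80 = 26.25 Gy; 21/0.70 = 30 Gy.

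All four table values are recovered, so the table follows directly from its normalization range.

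**Step 2: compare with the 130% cap.**

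| | Monotherapy | Boost |
|---|---|---|
| Cap, 1.30 x prescription | 47.13 Gy | 27.3 Gy |
| Table upper limit | 51.79 Gy | 30 Gy |
| Table upper limit / prescription | 142.9% | 142.9% |
| Table lower limit / prescription | 125% | 125% |
| Upper limit minus cap | about 4.7 Gy | 2.7 Gy |
| Upper limit / cap - 1 | 9.9% | 9.9% |

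**Step 3: find where the two rules part.** The cap is reached at a normalization of 1/1.30 = 76.9%. At 77% the maximum is 1/0.77 = 129.9% of prescription, inside the cap. At 76% it is 1/0.76 = 131.6%, outside. So 6.9 of the 10 percentage points that the table permits (70 to 76.9%) conflict with the clause. The remainder, up to 80%, satisfies both.

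**Step 4: the two monotherapy doses.** 7.27 x 5 = 36.35 Gy, and 36.25/5 = 7.25 Gy. The difference is 0.10 Gy in total and 0.02 Gy per fraction; 36.35/36.25 - 1 = 0.28%. With BED = total x (1 + dose per fraction / 1.5):
- 36.35 x (1 + 7.27/1.5) = 212.5 Gy
- 36.25 x (1 + 7.25/1.5) = 211.5 Gy

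The difference is about 0.5%.

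**Step 5: which dose the table was built on.**

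| Table limit (Gy) | Rule | On 36.25 | On 36.35 |
|---|---|---|---|
| 45.31 (PTV maximum, lower) | /0.80 | 45.31 | 45.44 |
| 51.79 (PTV maximum, upper) | /0.70 | 51.79 | 51.93 |
| 38.06 (rectum and bladder, 1 cc) | x 1.05 | 38.06 | 38.17 |
| 32.625 (rectum and bladder, 10%) | x 0.90 | 32.625 | 32.715 |
| 29 (rectum, 20%) | x 0.80 | 29.0 | 29.08 |
| 18.125 (rectum and bladder, 50%) | x 0.50 | 18.125 | 18.175 |

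Each limit fits 36.25 and none fits 36.35. Section 1.12 agrees and is the only place where 7.25 Gy is given as a five-fraction dose. The 6-7.25 Gy entries in Tables 1 and 2 belong to a six-fraction HDR series.

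**The case against.** The strongest reply on the PTV maximum is that the clause states a limit while the table lists objectives, so the limit simply binds within the wider range. That is a reasonable reading, but the protocol does not state it, and on that reading most of the table's normalization range would be forbidden. The two rules can also be met together, so no planner is forced into a breach. That stands, and it rules out the stronger inference a reader might draw, that planners cannot produce or recognize a compliant plan.

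A second reply is procedural. Section 8.4.2.1 requires a benchmark plan, reviewed by the principal investigator and physics chair, before enrollment, and section 11 describes enrollment at one site. Those reviewers could find the conflict and settle it. The review does not amend the text, however, and a benchmark plan normalized at 77-80% would not expose the problem.

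On the dose, one can say that planners work from 8.4, where the prescription clause and table agree, so the figure in 8.1 would rarely be used. That also stands and is why this part is editorial.

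A reader might also infer that patients were exposed to harmful hot spots, or that the efficacy results are compromised. The documents support neither. The table sets separate urethra, rectum and bladder limits, and nothing in section 11 uses either figure.

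**Conclusion.** Both inconsistencies are in the current text and nothing expressly reconciles them. They are wrong as written and minor.

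The PTV maximum is the more substantive: a gap of about 4.7 Gy (monotherapy) or 2.7 Gy (boost), 9.9% above the cap, for plans at the bottom of the permitted normalization range. The documents do not show which ceiling was intended. The calculation assumes that normalization is the prescription isodose as a fraction of the PTV maximum, which the table's own values bear out.

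The dose in 8.1 differs by 0.28% and applies to monotherapy only. That 36.25 Gy is the intended figure is an inference, but a strong one, because the prescription clause, the column heading, the scaled limits and the cited precedent all agree on it.

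The sample sizes (32 and 40), the bDFS definitions and the section 11 analyses are unchanged.

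**What to change.** 1. **PTV maximum.** Keep the stricter stated cap of 130%. In the 8.4.4.3 table, set normalization to 77-80% and the PTV maximum to 45.31-47.13 Gy (monotherapy) and 26.25-27.3 Gy (boost). If the investigator and physics lead confirm that 70-80% normalization was intended, change the cap in 8.4.4.1 to 143% instead and leave the table as it is. Until that is decided, planning at 77-80% meets both rules.
2. **Monotherapy dose.** Change 8.1 to 36.25 Gy (7.25 Gy x 5).

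The cost is protocol wording: one dose entry in 8.1, and either one clause or two table rows in 8.4.4. The only judgement needed is the choice of PTV ceiling. No change to sample size, data collection or analysis follows.
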